### **11.1.3 Progression Free Survival**

Time to progression (TTP), progression-free (PFS) survival, and overall survival (OS) will be determined, but are not primary study endpoints. Patients will be followed for progression free survival beginning with C1D1 of pembrolizumab on this trial through the date of progression, or death, whichever comes earlier. Progression will be assessed by irRECIST. Patients will be followed for survival endpoints every 6 months for 4 years following study enrollment.

## **11.2 Safety**

Routine safety and tolerability will be evaluated from the results of reported signs and symptoms, scheduled physical examinations, vital sign measurements, and clinical laboratory test results. More frequent safety evaluations may be performed if clinically indicated or at the discretion of the investigator.

### Physical Examination:

Complete and symptom-directed physical examinations will be performed by a licensed physician (or physician's assistant or nurse practitioner).

### Vital Signs:

Vital signs (blood pressure, respiratory rate, pulse rate and temperature) will be obtained.

### Safety Laboratory Determinations:

Laboratory evaluations will be performed as noted in the flow chart.

### **11.3 Stopping Rules**

Up to a total of 34 response evaluable patients are required. Generally, evaluable patients should have baseline scans and one 6 week follow-up scan to be evaluable for response assessment. Patients should also have received at least 2 cycles of Pembrolizumab to be considered evaluable for response. Enrollment and evaluation of response based on irRECIST.

An initial analysis will be done on the first 13 response evaluable patients enrolled to the Pembrolizumab treatment regimen. Recruitment will be terminated (stopped) if there are only 0 – 1 responses (irCR/irPR). If there are 2+ responses in 13 evaluable patients, recruitment will be expanded with this treatment regimen to up to an additional 21 evaluable patients.

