### **4.2 Number of Patients**

A total of 34-40 subjects will be recruited to one treatment arm in this study with the goal of enrolling 34 evaluable patients (defined in sections 11.1 and 11.3).

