#### **4.4 Study Duration**

We would anticipate that on average, patients will remain on treatment approximately 24 weeks (range of 2 to 52 weeks comparatively). However, patients may remain on treatment pembrolizumab for up to 2 years as long as they are receiving clinical benefit (SD, PR, CR), or until irRECIST progressive disease (PD) is confirmed. Confirmation of progression will occur 4-6 weeks after first detection prior to subject coming off study.

Accrual is anticipated to take 24-30 months. Estimated duration of accrual and patient participation is approximately three and half years.

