## **11 CRITERIA FOR EVALUATION AND ENDPOINT**

### **11.1 Efficacy**

Disease assessments will be measured by CT or MRI scan and assessed according to Immune related RECIST (irRECIST) based on Nishino et. al. (21)

Response rate is the primary response objective. Generally, evaluable patients should have baseline scans and one 6 week follow-up scan to be evaluable for response assessment. Patients should also have received at least 2 cycles of Pembrolizumab to be considered evaluable for response.

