### **Response Categories:**

- **Complete Response (irCR):** disappearance of all not-nodal target lesions and non-target lesions in two consecutive observations not less than 4 weeks apart. In addition, any pathological lymph nodes assigned as target lesions must have a reduction in short axis to  $<10\text{mm}$  (sum of diameters may be greater than zero at the time of CR, if nodal lesion are including as target lesions).
- **Partial Response (irPR):** at least a 30% decrease in the sum of diameters of all target lesions including new target lesion in two consecutive observations not less than 4 weeks apart, taking as reference the baseline sum of diameters.

- **Progressive Disease (irPD):** at least a 20% increase in the sum of diameters of all measured target lesions including new measurable lesions. The reference for irPD will be the smallest sum of diameter of all target lesions recorded at original baseline or subsequent. Progression must be confirmed with a follow up scan no less than 4 weeks and no more than 8 weeks after the first scan that shows disease progression.
- **Stable Disease (irSD):** neither a sufficient shrinkage to qualify of irPR or irCR, or an increase in the sum of target lesions which would qualify for irPD.

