### **11.1.2 Evaluation of Best Overall Response**

The best overall response is the best response observed until progression/recurrence and is determined as indicated in the table below:

Target Lesions	Non-Target Lesions	Evaluation of New Lesions	Best Overall Response
CR	CR	No	CR
CR	SD	No	PR
PR	Non-PD	No	PR
SD	Non-PD	No	SD
PD	Any	Yes or No	PD
Any	PD	Yes or No	PD
Any	Any	Yes	PD

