## **12 STATISTICAL CONSIDERATIONS**

A Simon Optimum Two-Stage design will be used with a Type I error rate alpha equal to 0.10 and a Type II error rate beta equal to 0.20. The null hypothesis is an objective response rate (irCR + irPR) of 10% or lower. The alternative hypothesis is an objective response rate of 25% or higher. With these design parameters, the first stage will consist of 13 patients. If there are 2 or more responses in 13 patients, up to an additional 21 evaluable patients will be recruited for a maximum sample size of 34 evaluable patients. If there are 6 or more responses in up to 34 evaluable patients the null hypothesis will be rejected. If there are 5 or fewer responses 34 evaluable patients the null hypothesis will not be rejected. It is estimated that it may be necessary to enroll up to 40 patients to accrue 34 response evaluable patients.

Kaplan-Meier methods and associated confidence intervals will be used to analyze PFS and OS. All subjects assessed for progression will contribute to this analysis. The clinical benefit rates (irCR + irPR + irSD) will be analyzed by tabulating the observed counts and proportions together with exact binomial confidence intervals.

Tumor tissue will be analyzed for the correlation of biomarkers to response rate.

- 1) Tissues analyzed for correlation of tumor mutational burden will be categorized as high, medium and low burden.
- 2) Tissues analyzed for correlation of PD-L1 expression will be categorized as high or low.
- 3) Tissues analyzed for correlation to proliferative index will be categorized as Ki-67 20-55% or Ki-67 > 55%.

Fisher's exact test will be used to analyze each of these biomarkers. Two sided p-values < 0.05 will be regarded as statistically significant.

Safety will be analyzed by tabulating adverse events.

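### Does the missing data cut-off for the stage-1 look cost the two-stage design its 80% power?

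*Combined protocol and SAP*

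**What the plan says.** - **Who is counted.** Section 4.2 sets recruitment "with the goal of enrolling 34 evaluable patients (defined in sections 11.1 and 11.3"). Section 11.1 gives the test: "Generally, evaluable patients should have baseline scans and one 6 week follow-up scan to be evaluable for response assessment", plus at least two cycles of treatment. Section 11.3 repeats it.
- **What a response is.** Section 11.3 evaluates response by irRECIST and counts irCR and irPR. Section 11.1.1 grants irPR only for a reduction seen "in two consecutive observations not less than 4 weeks apart, taking as reference the baseline sum of diameters". irCR carries the same two-observation requirement. Section 11.1.2 adds: "The best overall response is the best response observed until progression/recurrence".
- **When scans happen.** Footnote 10 of the Study Calendar (Section 9) sets CT every 6 weeks through cycle 12, then every 12 weeks.
- **The rule.** Section 11.3: "An initial analysis will be done on the first 13 response evaluable patients enrolled to the Pembrolizumab treatment regimen". Recruitment ends with 0-1 responses. Section 12: "If there are 2 or more responses in 13 patients, up to an additional 21 evaluable patients will be recruited". The null is rejected with 6 or more responses in 34.
- **The error rates.** Section 12 states a "Type I error rate alpha equal to 0.10 and a Type II error rate beta equal to 0.20" for response rates of 10% against 25%.

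The plan gives no data cut-off for the look and does not say how a patient awaiting a confirmatory scan is scored.

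**The concern.** Two different data minimums feed one count. A patient enters the 13 at week 6 but, on the planned schedule, cannot be a confirmed responder before about week 12. If the look were triggered by the 13th patient's week-6 scan, the last patients to enter would sit in the denominator with no chance of adding to the numerator. The design's power is only about one point above its 80% target, so one such patient is enough to break the stated beta. The result would be a higher chance of stopping an active drug after 13 patients.

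The wait also has no written limit. Best response runs to progression, and Section 4.4 expects that "patients will remain on treatment approximately 24 weeks (range of 2 to 52 weeks comparatively"). The trial is open label, so an unwritten cut-off would be chosen with the responses in view.

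**Working it through.** **Inputs.** Section 12: p0 = 0.10, p1 = 0.25, n1 = 13, continue with 2 or more responses, n = 34, reject with 6 or more. Section 4.4: accrual over 24-30 months. Section 9: scans every 6 weeks. Section 11.1.1: confirmation at 4 weeks or later.

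**1. The plan's own figures.** With X1 the responses among the first 13,

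P(reject) = sum over x from 2 to 13 of P(X1 = x) × P(Bin(21, p) ≥ 6 − x).

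- p = 0.25: 0.811.
- p = 0.10: 0.0957.
- Stopping probability at 25%: 0.75^13 + 13 × 0.25 × 0.75^12 = 0.0238 + 0.1029 = 0.127.
- Stopping probability at 10%: 0.9^13 + 13 × 0.1 × 0.9^12 = 0.2542 + 0.3672 = 0.621.
- Expected size under the null: 13 + (1 − 0.621) × 21 = 20.95.

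A search over designs confirms that this is the Simon optimum for the stated inputs. The boundaries are right.

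**2. A look that does not wait.** Suppose m of the 13 are pending and scored as failures at the look, with their true outcomes counted in the final 34. Then 13 − m replaces 13 in the first term, 34 − (13 − m) replaces 21 in the second, and the sum runs from 2 to 13 − m.

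| m | Wrongful stop at 25% | Power | Type I error |
|---|---|---|---|
| 0 | 0.127 | 0.811 | 0.096 |
| 1 | 0.158 | 0.785 | 0.090 |
| 2 | 0.197 | 0.753 | 0.083 |
| 3 | 0.244 | 0.712 | 0.076 |

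**3. How many would be pending.** With 52.18/12 weeks per month, 34 patients in 24 months is one every 24 × 52.18/12 ÷ 34 = 3.07 weeks. In 30 months it is one every 3.84 weeks. At the 13th patient's week-6 scan, patient 12 is 3.07-3.84 weeks ahead and patient 11 is 6.14-7.67 weeks ahead. With even spacing, m = 2 for a 4- or 6-week confirmation gap, and power is 75.3%.

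That value is fragile:
- At 30 months patient 12 is 26.9 days ahead, against a 28-day gap. At 24 months patient 11 is 43.0 days ahead, against a 42-day gap. Each case turns on about one day, inside the calendar's ±3-day cycle window and 7-day scan window.
- With random arrivals, for 34 or 40 patients over 24-30 months, average power is 68.7-72.4% for a 6-week gap and 72.5-74.7% for a 4-week gap.
- The 75.3% assumes that every responder already responds at week 6. If 25% or 50% first respond at week 12 (an assumption), it is 73.2% or 71.0%.
- If an unconfirmed week-6 response counted at the look and all responders showed by week 6, power would be 81.1%.

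**4. A look that waits, but not to the end.** Suppose each eventual response among the 13 is unseen at the cut-off with probability f. The documents give no time to response, so f is an assumption.

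| f | Power | Type I error |
|---|---|---|
| 0 | 0.811 | 0.096 |
| 0.031 | 0.800 | 0.093 |
| 0.05 | 0.793 | 0.092 |
| 0.10 | 0.772 | 0.088 |
| 0.20 | 0.720 | 0.078 |

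**5. What the text supports.** The losses in step 2 need two things that the plan does not state: that the look falls at the 13th patient's week-6 scan, and that pending patients are failures. The one-scan rule is a condition for entering the denominator. The numerator is irCR and irPR, which 11.1.1 defines by two observations. Taken together, a pending patient's outcome is not yet known, and the ordinary course is to obtain the next scan. On schedule, a response first seen at week 6 is confirmed at week 12, 6 weeks later. Continuing does not need all 13 outcomes: once two responses are confirmed, the condition in Section 12 is met.

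**The case for a change.** The best argument for a change is that waiting is not a complete answer, because it does not say how long. Best response runs to progression, so a patient with stable disease stays open, and any practical cut-off may miss a late first response. With about one point of slack, missing just over 3% of eventual responses takes power below 80%. A sentence in 11.3 would cost little and would fix the cut-off before responses are seen.

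Part of this stands. The plan is silent, and a sentence would make it clearer. But the documents give nothing on time to response, so they cannot show that the 3% threshold would be crossed or which follow-up would be long enough. That choice belongs to the sponsor, and so does the choice to hold enrolment. On enrolment, Section 12 read literally recruits the further 21 only after two responses, and Section 13 requires a slot to be confirmed before consent, so accrual can be held.

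The worry about an open-label choice of cut-off is limited. If the boundary is honoured on the first 13, the type I error is highest, at 0.0957, when all outcomes are known, and every earlier cut-off lowers it. It would pass 0.10 only if the stage-1 rule were ignored altogether (0.119 for 6 or more of 34 with no look). That would be a departure from the plan and has nothing to do with the timing of the look.

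**Conclusion.** The concern is right that one scan makes a patient evaluable, that a response needs two observations, and that no cut-off is written. It does not show an error in the design. The 2/13, 6/34 rule is the correct Simon optimum, with exact power 81.1% and type I error 0.096, and it keeps both when the look waits for the 13 outcomes.

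The fall to roughly 69-79% belongs to a look at the 13th patient's week-6 scan with pending patients scored as failures. The plan prescribes neither. The lower end rests on random arrivals at the planned accrual rates, and the upper end on a single pending patient with all responders showing at week 6. Type I error is not inflated under any of these readings.

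The gap is one that analysts fill sensibly from the plan's own response definition, by awaiting confirmatory scans before stopping for 0-1 responses. How far a late first response could still erode power after that wait cannot be judged from these documents. No change follows.

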## **12 STATISTICAL CONSIDERATIONS**

A Simon Optimum Two-Stage design will be used with a Type I error rate alpha equal to 0.10 and a Type II error rate beta equal to 0.20. The null hypothesis is an objective response rate (irCR + irPR) of 10% or lower. The alternative hypothesis is an objective response rate of 25% or higher. With these design parameters, the first stage will consist of 13 patients. If there are 2 or more responses in 13 patients, up to an additional 21 evaluable patients will be recruited for a maximum sample size of 34 evaluable patients. If there are 6 or more responses in up to 34 evaluable patients the null hypothesis will be rejected. If there are 5 or fewer responses 34 evaluable patients the null hypothesis will not be rejected. It is estimated that it may be necessary to enroll up to 40 patients to accrue 34 response evaluable patients.

Kaplan-Meier methods and associated confidence intervals will be used to analyze PFS and OS. All subjects assessed for progression will contribute to this analysis. The clinical benefit rates (irCR + irPR + irSD) will be analyzed by tabulating the observed counts and proportions together with exact binomial confidence intervals.

Tumor tissue will be analyzed for the correlation of biomarkers to response rate.

- 1) Tissues analyzed for correlation of tumor mutational burden will be categorized as high, medium and low burden.
- 2) Tissues analyzed for correlation of PD-L1 expression will be categorized as high or low.
- 3) Tissues analyzed for correlation to proliferative index will be categorized as Ki-67 20-55% or Ki-67 > 55%.

Fisher's exact test will be used to analyze each of these biomarkers. Two sided p-values < 0.05 will be regarded as statistically significant.

Safety will be analyzed by tabulating adverse events.

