## 2.4 Prognosis and Treatment

While most NETs are relatively slow-growing (G1 or G2) with a median survival of many years, the prognosis of patients with poorly differentiated G3 NECs is dismal with a median

survival of approximately 12 months (2). Common sites of metastases include liver, lung, bones, and brain. Histologically, poorly differentiated NECs can be classified as either “small cell” or “large cell” NEC. Clinically these entities behave very similarly and standard treatment for both large and small cell NEC is usually identical, although some practitioners favor temozolomide-based chemotherapy regimens over platinum-based regimens in patients with poorly differentiated NEC with Ki-67 <55% (2).

As this is a relatively rare patient population, large-scale, randomized phase III trials have been very difficult to perform. Standard accepted therapies have been extrapolated from experience in the treatment of SCLC or are based on smaller phase II trials in this specific population. First-line treatment generally involves chemotherapy, either platinum-based (e.g. carboplatin or cisplatin in combination with etoposide) or temozolomide-based (e.g. single-agent temozolomide, capecitabine + temozolomide). Response rates range from 10 – 70% but are generally not durable with no standard second-line treatment (2-4). Extrapolating from treatment algorithms used in small cell lung cancer (SCLC), chemotherapy is often administered in the second-line setting with disappointingly low response rates and early clinical progression (5-7).

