- 7 If clinically indicated, and not previously performed, tumor mutation burden analysis will be performed at central lab. If performed, results should be collected for the study. See section 15.
- 8 Patients must have existing Ki-67 results from archival tissue or available tissue for Ki-67 testing. If no archival tissue is available the subject must agree to a fresh biopsy for testing to qualify for the study. Ki-67 analysis will be performed at local lab if not previously performed. See section 15.
- 9 ECG will be done if medically indicated
- 10 CT of the abdomen/chest/pelvis must be repeated every 6 weeks through C12 (36 weeks), then every 12 weeks until disease progression. Progression must be confirmed no earlier than 4 weeks and no later than 8 weeks. Scans must be completed within 7 days prior to the next dosing cycle.
- 11 Pembrolizumab 200 mg IV q3weeks
- 12 Follow-up should occur no less than every 6 months for 4 years following study enrollment
- 13 Baseline procedures do not need to be repeated if screening procedures have been done within 7 days of start of treatment
- 14 MRI may be required at baseline for subjects with previously treated brain metastases

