### **16.6.2 Serious Adverse Event (SAE)**

Information about all serious adverse events will be collected and recorded. A serious adverse event is an undesirable sign, symptom or medical condition which:

- Is fatal or life-threatening
- Results in persistent or significant disability/incapacity
- Is medically significant, i.e., defined as an event that jeopardizes the patient or may require medical or surgical intervention to prevent one of the outcomes listed above
- Causes congenital anomaly or birth defect
- Requires inpatient hospitalization or prolongation of existing hospitalization, unless hospitalization is for:

- Routine treatment or monitoring of the studied indication, not associated with any deterioration in condition (procedures such as central line placements, paracentesis, pain control)
- Elective or pre-planned treatment for a pre-existing condition that is unrelated to the indication under study and has not worsened since the start of study drug
- Treatment on an emergency outpatient basis for an event not fulfilling any of the definitions of a SAE given above and not resulting in hospital admission
- Social reasons and respite care in the absence of any deterioration in the patient's general condition

Collection of serious adverse events will begin after the first dose and end 90 days after the last dose of study treatment or until a new cancer treatment is initiated, whichever happens the soonest.

Any death from any cause while a patient is receiving treatment on this protocol or up to 30 days after the last dose of protocol treatment, or any death which occurs more than 30 days after protocol treatment has ended but which is felt to be treatment related, must be reported.

Toxicities which fall within the definitions listed above must be reported as an SAE regardless if they are felt to be treatment related or not. Toxicities unrelated to treatment that do NOT fall within the definitions above, must simply be documented as AEs in the patient research chart.

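### The only PFS/OS population named in section 12 is subjects assessed for progression, which on a plain reading leaves out patients who die before any post-baseline scan and contradicts section 11.1.3

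*Combined protocol and SAP*

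**What the plan says.** Section 12 gives the method: "Kaplan-Meier methods and associated confidence intervals will be used to analyze PFS and OS". The next sentence gives the population: "All subjects assessed for progression will contribute to this analysis". It therefore covers both endpoints, and nothing else in the protocol names a population for either. The evaluability rule in sections 11.1 and 11.3 (baseline scan, one 6-week scan, at least two cycles) is for response only.

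Section 11.1.3 defines PFS as running "beginning with C1D1 of pembrolizumab on this trial through the date of progression, or death, whichever comes earlier". It adds: "Progression will be assessed by irRECIST". It also follows patients for survival every 6 months for 4 years and sets no imaging condition.

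The section 9 calendar puts the first on-treatment CT at C3, and footnote 10 says: "Scans must be completed within 7 days prior to the next dosing cycle". The calendar also marks CT and irRECIST at End of Treatment, although the list in section 10.3 omits the scan. No censoring rule for PFS or OS appears anywhere.

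**The concern.** Progression under irRECIST is a change in lesion measurements on a follow-up scan, so a baseline scan alone cannot show it. A patient who dies on day 25 without another scan has a PFS event and an OS event under section 11.1.3, but does not belong to the section 12 set.

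The clock starts at C1D1 while entry to the analysis depends on reaching a later scan. Everyone included is then guaranteed to survive to that scan, and removing the earliest deaths biases the curves upward. The condition is hardest to defend for OS, which needs no imaging.

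PFS and median OS are secondary objectives 1.2.2 and 1.2.3. In a single-arm study no control group offsets such a selection. As the plan stands, two analysts could defend different sets.

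**Working it through.** **The plan's own figures.** There is no event count, sample size or power for PFS or OS to reproduce. The response design does reproduce: 1/13 then 5/34 has exact type I error 0.0957 at a 10% response rate and power 0.8108 at 25%. Nothing below changes it. The plan allows up to 40 enrolled for 34 evaluable, so up to 6 of 40 (15%) may be non-evaluable. That covers every reason for non-evaluability and is not an estimate of early deaths.

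**When the first scan falls.** C3 dosing is two 21-day cycles after C1D1, that is day 42. The scan may be up to 7 days earlier, so t₀ is day 35 to 42. At 30.4375 days per month that is 1.15 to 1.38 months.

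**Effect on the curve, whatever the survival distribution.** If k of 40 treated patients die before a scan and are dropped, with no earlier censoring, every later estimate is multiplied by 40/(40−k).

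| k dropped | Factor | A value of 50% reads as |
|---|---|---|
| 1 | 1.026 | 51.3% |
| 3 | 1.081 | 54.1% |
| 6 | 1.176 | 58.8% |

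**OS illustration.** Assume exponential survival with median m, and that all deaths before t₀ are dropped. The dropped share is e = 1 − 0.5^(t₀/m). The reported median solves S(t) = 0.5(1 − e), which gives t₀ + m. The 12-month median is from section 2.4 ("survival of approximately 12 months") and is not specific to previously treated patients. The 6-month median is an assumption outside the documents.

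| Median m | t₀ | Dropped share e | Of 40 | Reported median |
|---|---|---|---|---|
| 12 months | day 35 | 6.4% | 2.6 | 13.15 months |
| 12 months | day 42 | 7.7% | 3.1 | 13.38 months |
| 6 months | day 35 | 12.4% | 5.0 | 7.15 months |
| 6 months | day 42 | 14.7% | 5.9 | 7.38 months |

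These are upper-end cases, because some patients who stop early will have an End of Treatment scan. If only half of the deaths before day 42 lack a scan and m = 12, then e = 3.83%. Solving 0.5^(t/12) = 0.5 × 0.9617 gives t = 12.68 months.

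**PFS illustration.** Assume death is exponential with median 12 months and progression is exponential with an assumed median p, detected only at 6-week scans. After the scan at time g, PFS is 0.5^(g/p) × 0.5^(t/12). The last scan before 6 months is at day 168 (5.52 months). Dropping all deaths before day 42 divides later values by 1 − 0.0766 = 0.9234.

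- p = 2 months, 6-month PFS: 0.5^(5.52/2) × 0.5^(6/12) = 10.4%, which becomes 10.4/0.9234 = 11.3%. The median stays at 2.76 months, because both curves cross 50% at the second scan (52.9% to 32.8% with all patients, 57.2% to 35.5% after dropping).
- p = 4 months, 6-month PFS: 0.5^(5.52/4) × 0.5^(6/12) = 27.2%, which becomes 27.2/0.9234 = 29.4%. The median with all patients is 12 × log₂(0.6199/0.5) = 3.72 months. After dropping, the curve first falls below 50% at the third scan, 4.14 months.

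**The case against.** The sentence says who contributes and does not say only those subjects. It follows a paragraph that limits the response analysis to 34 evaluable patients out of up to 40, so it may have been meant to widen the set. Section 11.1.3 already makes death an event from C1D1, and the two sections could be read together. Where the authors wanted a scan requirement, for response, they wrote one. The End of Treatment scan also shrinks the affected group to patients with no post-baseline scan at all.

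On size, k is unknown, three of the medians used above are assumptions, and a constant hazard may overstate early deaths when entry requires ECOG 0 or 1. With 40 patients and no censoring, the standard error at 50% is √(0.25/40) = 7.9 points, and under the exponential model with a 12-month median the sample median ranges from roughly 7.5 to 18 months. The shifts lie well inside that range.

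Most of this stands as a limit on size. It does not remove the problem. Sampling error is shown by the confidence interval; a shift caused by the choice of set is not, and its direction is known. If the intent was to widen the set, the text does not say so, and anyone applying it as written would drop early deaths from OS as well as PFS.

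**Conclusion.** The concern holds and should be fixed. As written, the section 12 population is wrong for OS and inconsistent with the plan's own PFS definition, and the error favours the treatment. Its size depends on how many patients die with no post-baseline scan, which the documents do not say. One to six of 40 inflates later curve values by about 3% to 18%. On the 12-month median, OS would read roughly 0.7 to 1.4 months too long, given exponential survival and half to all of the pre-scan deaths lost. For PFS, the median moves by 0 to 0.4 months and the 6-month rate by 1 to 2 points under the assumed progression rates. PFS and OS are secondary, no decision rule uses them, and the primary response analysis is untouched. The missing censoring rules are a related gap, best closed at the same time.

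**What to change.** Replace the population sentence in section 12 with text such as:

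> All patients who receive at least one dose of pembrolizumab contribute to PFS and OS, measured from C1D1. Death without a prior post-baseline assessment is an event for both endpoints. Patients alive without progression are censored for PFS at the last adequate disease assessment (at C1D1 if there is no post-baseline scan) and for OS at last contact.

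The plan should also say what counts as an adequate assessment. The change should be made before PFS and OS are analysed, so that the set is not chosen with the results in view.

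The cost is a few sentences and no new visits or data. Section 16.6.2 already requires reporting of "Any death from any cause while a patient is receiving treatment on this protocol or up to 30 days after the last dose", and section 11.1.3 already follows patients for survival. The only downside is that the reported curves may be slightly less favourable.
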